2.1.3 Premature Discontinuation/Early termination

For each premature discontinuation, the following parameters will be listed: subject number, sequence, and the reason of premature discontinuation.

2.1.4 Protocol Deviations

Protocol deviations will be listed with subject number, date and description of protocol deviation in the final report.

2.2 Effectiveness/Efficacy analysis

2.2.1 Primary Outcome:

The primary outcome is the change in whole blood NAD⁺ levels from baseline to day 8 when supplemented with RiaGev™ or comparator.

The primary null hypothesis is as follows:

H₀: There is no significant difference in mean change in NAD⁺ level from pre-supplementation to post-supplementation, between subjects taking RiaGev™ or comparator.

Possible differences before exercise from day 1 to days 3, 5 and 8 between the study groups will be assessed using repeated-measures mixed ANCOVA. The model will include treatment, visit number, sequence and period as fixed effects and subject as a random effect. Between group p-values will be obtained from this model, while within group p-values will be obtained using paired t tests or Wilcoxon Signed Rank test as appropriate.

Possible differences at after exercise from day 1 to day 8 between the study groups will be assessed using repeated-measures mixed ANCOVA. The model will include treatment, visit number, sequence and period as fixed effects and subject as a random effect. Between group p-values will be obtained from this model, while within group p-values will be obtained using paired t tests or Wilcoxon Signed Rank test as appropriate.

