11.3 Statistical Analysis Plan

The primary outcome is the change in whole blood NAD+ levels from baseline to day 6 compared between $RiaGev^{TM}$ and comparator.

An effectiveness analysis based on the intent-to-treat population and an efficacy analysis based on the per protocol population will be performed. Safety analysis will be done for the safety population.

Variables will be tested for normality and transformed to the log scale if found to be non-normally distributed. Log-normally distributed variables will be analyzed in the logarithmic domain. Intractably non-normal outcome variables will be analyzed by appropriate non-parametric tests.

Missing values in the intent-to-treat and per protocol analyses will be imputed using the most recent previously-available value (LOCF, or "last-observation-carried-forward" imputation) or multiple imputation methods. No imputation will be performed for missing safety values.

For each continuous endpoint, a summary table will be prepared with a variety of summary statistics including mean, standard deviation, median and range values for each time point-treatment pairing. To account for any a priori differences between groups, the summary statistics of the changes from baseline will also be provided. For parameters requiring a logarithmic transformation, the summary statistics will be provided as non-transformed values. Mean values will be displayed as graphs, with a separate line for each product, and error bars indicating standard errors or standard deviations. Mean changes from baseline will be graphed similarly. Although imputed data will be used for significance testing, non-imputed data will be used for presenting summaries. Categorical variables will be summarized as counts and percentages.

Continuous efficacy endpoints will be tested for significance between groups by Analysis of Covariance (ANCOVA). The dependent variable will be the measurement at each visit, the factor will be the treatment group, and the value at baseline (Day 1) will be the covariate. A within group analysis on effectiveness/efficacy endpoints will be done using the Student's paired t-test or, in the case of intractable non-normality, the Wilcoxon sign rank test. Categorical variables will be compared using Chi-squared or Fisher's Exact tests as appropriate.

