1.3 Primary Outcome

The primary endpoint is the change in whole blood NAD+ levels from baseline to day 8 when supplemented with RiaGev™ or comparator.

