2.4.5 Adjustments of Multiple Comparisons

Since there are only two study groups involved, there will be no pairwise comparisons requiring adjustment. There will be no adjustment for multiple outcomes.

3. Reference List

2. Mark Mather, Linda A. Jacobsen, Kelvin M. Pollard. Aging Baby Boomers to Face Caregiving, Obesity, Inequality Challenges [Internet]. population reference bureau; 2016 Jan. Available from: <https://www.prb.org/unitedstates-population-bulletin/>
3. Diabetes [Internet]. world health organization; 2018 Oct. Available from: <https://www.who.int/news-room/fact-sheets/detail/diabetes>
4. RiaGev® [Internet]. bioenergy life science Inc.; Available from: <http://bioenergylifescience.com/#products>
5. Compound Summary for CID 10975657 D-Ribose [Internet]. National Center for Biotechnology Information; [cited 2019 Feb 28]. Available from: <https://pubchem.ncbi.nlm.nih.gov/compound/D-ribopyranose#section=Food-Additives-and-Ingredients>
7. Niacin Fact Sheet for Health Professionals [Internet]. National Institutes of Health; 2019. Available from: <https://ods.od.nih.gov/factsheets/Niacin-HealthProfessional/#h9>

4. Appendix

Table 3. Summary of outcomes and analysis methods

Outcome	Data type	Between groups analysis methods
Primary Outcome		
1. The change in whole blood NAD+ levels from baseline to day 8 when supplemented with RiaGev™ or comparator.	Interval	Repeated-measures mixed ANCOVA
Secondary Outcomes		
1. The change in serum glucose and insulin as assessed by an Oral Glucose Tolerance Test (OGTT) at t=0, 15m, 30, 45m, 60m, 90m and 2h after a 7-day supplementation with either RiaGev™ or comparator	Interval	Repeated-measures mixed ANOVA (change in concentrations); mixed ANOVA (iAUC)
2. The change in serum Glutathione/Glutathione disulfide (GSH/GSSG) ratio after a 7-day supplementation with either RiaGev™ or comparator	Interval	Repeated-measures mixed ANCOVA
3. The change in serum adenosine triphosphate/ adenosine monophosphate (ATP/AMP) ratio after a 7-day supplementation with either RiaGev™ or comparator	Interval	Repeated-measures mixed ANCOVA

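### The SAP's primary NAD+ model tests an average over Days 3, 5 and 8 instead of the declared Day 8 endpoint, and it omits within-period correlation

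*SAP*

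**What the plan says.** - **Endpoint.** SAP 1.3: "The primary endpoint is the change in whole blood NAD+ levels from baseline to day 8". The primary row of SAP Table 3 repeats it ("The change in whole blood NAD+ levels from baseline to day 8"), and protocol section 5 agrees.
- **Null hypothesis.** SAP 2.2.1 compares the mean change "from pre-supplementation to post-supplementation" and names no day.
- **First primary analysis.** SAP 2.2.1: "Possible differences before exercise from day 1 to days 3, 5 and 8 between the study groups will be assessed", by a repeated-measures mixed ANCOVA. Its terms are given as "The model will include treatment, visit number, sequence and period as fixed effects and subject as a random effect", and the between-group p-values come from that model.
- **Second primary analysis.** The same terms are used for "Possible differences at after exercise from day 1 to day 8 between the study groups".
- **Baseline.** The SAP calls the model ANCOVA but names no covariate. SAP 2.1 defines change scores against the pre-supplementation value. Protocol 11.3 says "The dependent variable will be the measurement at each visit" and "the value at baseline (Day 1) will be the covariate".
- **Samples.** At Visits 2, 5, 6 and 9 (protocol 9.3, 9.6, 9.8, 9.11) the only listed NAD+ draw comes two hours after the meal and before the treadmill. The tube listed after the treadmill is for GSH/GSSG and ATP/AMP.

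**The concern.** There are two separate faults in the first primary model.

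The first is the question it answers. A main-effects model with three post-dose visits gives one treatment coefficient for all of them. The trial could be declared positive on early effects that have gone by Day 8, or miss a Day 8 effect that was diluted by earlier visits. Neither result would answer the endpoint sentence.

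The second is the standard error. Each participant receives one treatment per period, so the unit that carries treatment is the participant-period. A random subject effect covers only correlation common to all of a participant's visits. If visits within a period are more alike than visits across periods, or if all rows of a period share one noisy Day 1 value, the model treats the three rows as more independent information than they are.

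**Working it through.** **1. The plan's own sizing.** Inputs from protocol 11.1: 18 participants, 20% loss, SD 11.04, 5% level (two-sided assumed), 80% power, difference 8.7. Completers: 18 × 0.8 = 14.4. If 11.04 is read as the SD of one within-participant difference, a paired t test detects 8.94 with 14 completers and 8.59 with 15. The stated 8.7 lies between them. The sizing therefore fits a single treatment difference per participant, not a pooled three-visit model.

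**2. What the pooled coefficient estimates.** With balanced data it is (δ3 + δ5 + δ8)/3. Set δ8 = 8.7 and assume a time course:

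| Assumed course | Pooled target |
|---|---|
| Effect at Day 8 only | 8.7/3 = 2.9 |
| In proportion to doses taken: 4, 8, 14 (from protocol 8.5) | 8.7 × (4/14 + 8/14 + 1)/3 = 8.7 × 0.62 = 5.4 |
| Reached by Day 3 and held | 8.7 |

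Conversely, effects of 8.7, 8.7 and 0 give 17.4/3 = 5.8. In a change-score simulation with 18 participants the pooled model was then significant in 92% of trials, and a Day 8 test in 5%.

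**3. Standard error under the change-score reading.** Assume equal, independent visit errors of variance 1.
- Participant-period mean square: 3 × (1/3 + 1) = 4, on 18 − 2 = 16 df.
- Visit-within-period mean square: 1, on 36 × 2 − 2 = 70 df.
- The model pools them: (4 × 16 + 1 × 70)/86 = 1.558.
- The standard error is too small by a factor √(4/1.558) = 1.60, and the actual size of a nominal 5% test is about 22%. The shared Day 1 value alone produces this.

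**4. False-positive rates by simulation.** Null trials, 9 participants per sequence, random-intercept REML. Visit error variance is 1. Assumed grid: subject variance 0.25 to 5, subject-by-period variance 0 to 1, serial correlation 0, 0.3 or 0.6; 48 cells of 8,000 trials.

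| Reading | Serial 0 | 0.3 | 0.6 |
|---|---|---|---|
| Pooled, Day 1 covariate | 5.7–17.3% | 12.3–21.7% | 19.7–24.3% |
| Pooled, change scores | 21.2–23.3% | 23.0–25.2% | 24.9–26.8% |

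A Day 8 crossover test with that period's Day 1 value as covariate gave 4.8–5.8% over the whole grid. The same model at Day 3 or Day 5 gave 4.6–6.0%.

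**5. Precision of the Day 8 test.** These are ratios of true SDs, Day 8 covariate test to pooled estimate. With independent errors and no subject-by-period variance:
- against the pooled covariate reading, √(1/(1/3)) = 1.7;
- against the pooled change-score reading, √(1/(4/3)) = 0.87.

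Over the subject-by-period and serial-correlation values in step 4 the ranges are about 1.3–1.7 and 0.87–1.19.

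**The case against.** The best defence is that the null hypothesis names no day, so a pooled comparison is a legitimate reading and, if the effect is reached by Day 3 and held, estimates the Day 8 effect exactly. That is true, but it rests on a time course the plan does not claim, and three statements of the endpoint name Day 8. The by-visit ANCOVA in protocol 11.3 does not settle it either. The SAP does not carry it over, it has no period, sequence or subject term, and that section gives the endpoint day as 6.

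A second defence is that the word repeated-measures implies a covariance structure. None is stated, while the random effect is.

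Four stronger readings go further than the documents allow:

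- **The false-positive rate is certainly far above 5%.** The protocol gives one NAD+ SD and no split into subject, period and visit parts. In the most favourable cell of the covariate reading, which protocol 11.3 supports best, the rate is 5.7%.
- **The after-exercise NAD+ analysis has no sample.** The documents show only that no post-exercise NAD+ draw is scheduled. A post-exercise whole-blood tube is drawn, and protocol 9.14 sends it to the laboratory that also assays NAD.
- **Mixing sampling conditions biases the comparison.** Days 3 and 5 follow a home dose and Day 8 follows a clinic meal, but both treatments are sampled alike. This changes what the average means, not the fairness of the contrast.
- **A Day 8 test always loses precision.** It does against the pooled covariate reading. Against pooled change scores it can be the more precise.

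**Conclusion.** Wrong as written. The pre-exercise primary p-value does not test the declared Day 8 endpoint, and no other specified model with scheduled data does. This part follows from the text alone. How far the pooled target departs from the Day 8 effect (2.9 to 8.7 when that effect is 8.7) depends on assumed time courses.

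The omission of within-period correlation is also plain from the model terms, but its effect is conditional on variances the documents do not give: about 5–6% at best and up to 24% with a Day 1 covariate, and about 21–27% with change scores. The 22% change-score figure needs only equal, independent errors. The SAP does not say which of the two readings applies, and that should be settled in the same correction.

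**What to change.** 1. Name the Day 8 treatment contrast as the single primary test. Use one Day 8 NAD+ value per participant per period, with treatment, period and sequence fixed, that period's Day 1 NAD+ as covariate, and subject random.
2. State that Day 3 or Day 5 values are not carried forward into this test. SAP 2.4.1 permits last-observation-carried-forward in the intent-to-treat analysis, which would bring early visits back in.
3. Report Days 3 and 5 as supportive, each with the same one-value-per-period model. This needs no within-period covariance structure.
4. Reconcile the after-exercise NAD+ paragraph with the visit lists. Delete it or label it non-primary unless a post-exercise NAD+ assay is confirmed.
5. Make the same correction for salivary cortisol and CIS, which use the same terms. For CIS, first reconcile protocol 9.12.4 (questionnaire at Visits 2 to 8) with the schedule in 1.3 and section 9.11, which include Visit 9.

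The cost is SAP wording and no new data. The true SD rises about 1.3–1.7 times against the pooled covariate reading and changes by about 0.9–1.2 times against pooled change scores. The Day 8 test fits the planned sizing if 11.04 is the SD of the within-participant difference. SAP 1.8 describes enrolment in the past tense, so the change must be dated relative to unblinding.

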2.1 General Approach

The primary and secondary endpoints will be analysed for both ITT and PP population. Safety parameters will be analysed for Safety population. All data will be summarised by study group, visit and/or study week as specified in the study objectives.

For nominal variables, counts and percentages will be presented. The denominator for each percentage will be the number of participants within the study group at that visit unless otherwise specified.

For interval variables, the arithmetic mean, standard deviation, median and min-max range will be presented to two decimal places. This will be accompanied by the number of participants included in the analysis for that time point.

Changes in interval endpoints from pre-supplementation will be calculated as:

$$\text{Change to } V_i = \text{Value at } V_i - \text{Value at } V_{\text{pre-supplementation}}$$

P-values will be rounded to three decimal places. P-values less than 0.001 will be reported as <0.001. P-values less than or equal to 0.05 will be considered statistically significant. All analyses will be performed using R Statistical Software version 3.6.1 (R Core Team, 2019) for Microsoft Windows.

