2.2.2 Secondary Outcomes

1. The change in serum glucose and insulin as assessed by an Oral Glucose Tolerance Test (OGTT) at t=0, 15m, 30, 45m, 60m, 90m and 2h after a 7-day supplementation with either RiaGev™ or comparator.

The change in serum glucose and insulin will be represented as change in mean concentrations at each time point. Assessment of change in mean concentrations for each analyte will be conducted using repeated-measures mixed ANOVA. The model will include treatment, time, sequence and period as fixed effects and subject as the random effect. Between group p-values will be obtained from this model, while within group p-values (from day 1 to day 8) will be obtained using paired t tests or Wilcoxon Signed Rank test as appropriate. An incremental area under the curve (iAUC) will be calculated for each group and compared between groups using mixed ANOVA, with study group, sequence and period as fixed effects and subject as the random effect.

2. The change in serum Glutathione/Glutathione disulfide (GSH/GSSG) ratio after a 7-day supplementation with either RiaGev™ or comparator

Assessment of the change in the ratio from day 1 to day 8 will be conducted using repeated-measures mixed ANCOVA. The model will include treatment, sequence and period as fixed effects and subject as the random effect. Between group p-values will be obtained from this model, while within group p-values will be obtained using paired t tests or Wilcoxon Signed Rank test as appropriate.

3. The change in serum adenosine triphosphate/ adenosine monophosphate (ATP/AMP) ratio after a 7-day supplementation with either RiaGev™ or comparator

Assessment of the change in the ratio from day 1 to day 8 will be conducted using repeated-measures mixed ANCOVA. The model will include treatment, sequence and period as fixed effects and subject as a random effect. Between group p-values will be obtained from this model, while within group p-values will be obtained using paired t tests or Wilcoxon Signed Rank test as appropriate.

4. The change in salivary cortisol after a 7-day supplementation with either RiaGev™ or comparator

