Assessment of the change in the level of salivary cortisol from day 1 to days 3, 5 and 8 will be conducted using repeated-measures mixed ANCOVA. The model will include treatment, visit number, sequence and period as fixed effects and subject as the random effect. Between group p-values will be obtained from this model, while within group p-values will be obtained using paired t tests or Wilcoxon Signed Rank test as appropriate.

5. The change in Checklist Individual Strength (CIS) Questionnaire outcome after a 7-day supplementation with either RiaGev™ or comparator

The domains for this questionnaire are:

1. Subjective feeling of fatigue: sum of the scores for items 1, 4, 6, 9, 12, 14, 16, and 20
2. Concentration: sum of the scores for items 3, 8, 11, 13, and 19
3. Motivation: sum of the scores for items 2, 5, 15, and 18
4. Physical activity: sum of the scores for items 7, 10, and 17
5. Total: sum of the scores for the four sub-scales listed above

For item 2, 5, 6, 7, 8, 11, 12, 15, and 20, the score is 1 for “yes, that is true” and 7 for “no, that is not true”. For item 1, 3, 4, 9, 10, 13, 14, 16, 17, 18, and 19, the score is 7 for “yes, that is true” and 1 for “no, that is not true”.

Assessment of change in each CIS domain will be conducted using repeated-measures mixed ANCOVA. The model will include treatment, visit number, sequence and period as fixed effects and subject as the random effect. Between group p-values will be obtained from this model, while within group p-values will be obtained using paired t tests or Wilcoxon Signed Rank test as appropriate.

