2.4 Statistical and Analytical Issues

2.4.1 Handling of Dropouts and Missing Data

Missing values in the intention-to-treat analysis will be imputed using the last available value (“last-observation-carried-forward” (LOCF)) or multiple imputation methods as appropriate. No imputation will be performed for missing values in the per protocol or the safety populations.

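### The NAD+, cortisol, CIS and point-by-point OGTT models carry no within-period correlation beyond subject, so the treatment test runs above 5%

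*SAP*

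**What the plan says.** SAP 1.3 defines the endpoint: "The primary endpoint is the change in whole blood NAD+ levels from baseline to day 8". SAP 2.2.1 then models the before-exercise changes to Days 3, 5 and 8 together: "The model will include treatment, visit number, sequence and period as fixed effects and subject as a random effect". It takes the between-group p-values from that model.

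SAP 2.2.2 uses the same sentence for cortisol and CIS (items 4 and 5). For glucose and insulin at seven time points (item 1) it has "The model will include treatment, time, sequence and period as fixed effects and subject as the random effect".

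Three other passages bear on this:

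- SAP 2.1 analyses differences from the pre-supplementation value ("Changes in interval endpoints from pre-supplementation will be calculated as").
- SAP 2.2.1 calls the model an ANCOVA but lists no covariate. Protocol 11.3 says "the value at baseline (Day 1) will be the covariate", in a per-visit ANCOVA that has no subject term.
- SAP 2.4.1: "Missing values in the intention-to-treat analysis will be imputed using the last available value", with multiple imputation as an alternative.

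The significance rule is "P-values less than or equal to 0.05 will be considered statistically significant". The only model check, in SAP 2.4.4, concerns normality of residuals.

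**The concern.** With subject as the only random effect and nothing said about residuals, the model gives two records from the same period the same correlation as two records from different periods. Visit-to-visit scatter within a period then counts as error for treatment, although treatment never changes within a period. If records within a period are more alike than records across periods, the standard error is too small and the degrees of freedom too many.

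The plan builds in such likeness. All changes in a period subtract the same Day 1 measurement. LOCF copies one value to later visits. The seven OGTT changes in a period come from the same two curves.

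The primary p-value comes from this model, and the error favours declaring an effect on NAD+ where there is none. Because the model has no treatment-by-visit term, its treatment test also averages Days 3, 5 and 8, whereas the endpoint is Day 8.

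**Working it through.** **The plan's own figure.** Protocol 11.1 gives N = 18 for a difference of 8.7, SD 11.04, 5%, 80% power and 20% loss. Take 11.04 as the SD of the within-subject difference and use a paired t-test. With 15 evaluable subjects the noncentrality is (8.7/11.04) × √15 = 3.05 and power is 81.0%; 14 give 77.8%. Then 15 × 1.2 = 18 (15/0.8 = 18.75 would give 19). A two-sample formula needs 26 per arm. So the sample size matches a comparison of one value per subject per period.

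**Where treatment is tested.** Let m be the records per period. Set the within-subject variance to 1, and let ρ be the share of it common to all records of one subject in one period (the extra within-period ICC). With 18 subjects, complete data and no covariate:

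- Subject-by-period stratum, which carries treatment: 18 − 2 = 16 df, expected mean square 1 + (m − 1)ρ.
- Records within a period: (2 × 18 − 1)(m − 1) df, which is 70 for m = 3 and 210 for m = 7; expected mean square 1 − ρ.
- The subject-only model pools the two: P = [16(1 + (m − 1)ρ) + df₂(1 − ρ)] / (16 + df₂).
- The true standard error is k = √{[1 + (m − 1)ρ]/P} times the model's.
- Type I error ≈ 2[1 − Φ(c/k)], with c = 1.988 on 86 df or 1.971 on 226 df.

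| m | ρ | True mean square | Pooled P | k | Formula | Simulated |
|---|---|---|---|---|---|---|
| 3 | 0.2 | 1.4 | 0.912 | 1.24 | 10.9% | 12.0% |
| 3 | 0.4 | 1.8 | 0.823 | 1.48 | 17.9% | 18.0% |
| 3 | 0.5 | 2.0 | 0.779 | 1.60 | 21.5% | 20.7–21.4% |
| 3 | 0.6 | 2.2 | 0.735 | 1.73 | 25.1% | 25.4% |
| 7 | 0.1 | 1.6 | 0.950 | 1.30 | 12.9% | 13.0–13.7% |
| 7 | 0.3 | 2.8 | 0.849 | 1.82 | 27.8% | 28.0–29.1% |
| 7 | 0.5 | 4.0 | 0.748 | 2.31 | 39.4% | 39.0–40.2% |

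The row m = 3, ρ = 0.5 is the shared-baseline case. If Day 1 and later values have equal error variance σ², each change has variance 2σ² and two changes in a period have covariance σ². The correlation is therefore 0.5 even when the raw values have no extra within-period correlation.

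**With the Day 1 covariate** (null REML simulations, 9 per sequence, within-subject variance 1, 4000 runs per case). One slope has to serve both the between-subject and the within-subject relation, so part of the Day 1 error stays in every record of the period.

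| Extra ICC | 0 | 0.1 | 0.2 | 0.3 | 0.5 |
|---|---|---|---|---|---|
| Subject variance 1, Day 1 outside the period effect | 7.2% | 10.0% | 13.7% | 16.4% | 23.6% |
| Subject variance 1, Day 1 sharing it | – | 10.0% | 11.9% | 13.9% | 16.5% |
| Subject variance 3 | 9.8% | 12.9% | 15.5% | 18.5% | 24.3% |

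A separate set of 2000 runs per case, with correlation 0.5 across periods and 0.5, 0.6, 0.7 or 0.8 within, gave 7.8%, 11.8%, 14.5% and 18.3%. Since (0.6 − 0.5)/(1 − 0.5) = 0.2 and so on, these correspond to ρ = 0, 0.2, 0.4 and 0.6.

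**LOCF** from Day 3 to Days 5 and 8 in 0, 10 or 20% of subject-periods, at ρ = 0: 6.9%, 9.3%, 11.9% (subject variance 3: 9.9%, 12.0%, 14.4%).

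**OGTT with serial correlation** of 0.3, 0.5 or 0.7 between adjacent points: 13%, 24%, 36%.

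**Remedies.** Subject-by-period intercept on 15 df: 3.6–6.5% (800 runs). Day 8 alone with the Day 1 covariate: 4.9–5.5%. Day 8 contrast from a treatment-by-visit term at ρ = 0 to 0.3: 5.3–7.1% with subject only (1500 runs), 4.2–6.0% with subject-by-period added (600 runs).

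**The case against.** The strongest reply is that the SAP never states that the pooled treatment effect is the primary p-value. The endpoint is Day 8, and a Day 8 contrast from a subject-only model is only slightly high, at 5.3–7.1% (5–8% in a second set of runs). That is true of the contrast, but the listed terms contain no treatment-by-visit interaction, so the model as written cannot produce it.

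A second reply is that a repeated-measures model need not have independent residuals. The SAP gives the same label to GSH/GSSG and ATP/AMP, which have one change per period, so the label cannot stand for a within-period covariance.

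Some points about size stand:

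- The documents give no correlation or variance ratio. With the covariate, ρ = 0 and a subject variance of 0.25, the error is only about 5–6%.
- The 20% LOCF case is severe. The protocol's 20% refers to participants, and 20% of subject-periods would touch about 36% of subjects (1 − 0.8²). If 20% of subjects drop out between Days 3 and 5 of period 2, the error is about 9% (12% at subject variance 3). The SAP also allows multiple imputation and imputes nothing in the per-protocol set.
- The 21% figure needs a reading without a covariate, which the word ANCOVA and protocol 11.3 speak against.
- SAP 2.2.2 item 5 names no days for CIS, and protocol 9.12.4 stops CIS at Visit 8 while the schedule runs to Visit 9. Either way, several records per period are stacked.

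**Conclusion.** The concern holds and should be fixed before analysis. Fitted as written, the before-exercise NAD+ model tests treatment against an error that is too small whenever records within a period correlate more than records across periods. For 18 subjects with the Day 1 covariate, the two-sided type I error is 7–10% at no extra ICC, 10–13% at 0.1, 12–16% at 0.2, 14–19% at 0.3 and 17–24% at 0.5. These ranges assume subject variance of 1 or 3 times the within-subject variance; a lower subject variance brings the first figure close to 5%. Without the covariate, change scores give about 21% from the shared baseline alone, if error variances are equal.

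The three-visit figures apply equally to cortisol and to CIS if CIS is analysed at the same visits. The point-by-point OGTT tests are worse: 13–14%, 20–21%, 28–29% and 39–40% at ICC 0.1, 0.2, 0.3 and 0.5.

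The direction and mechanism are certain; the size is a range because the ICCs, variances and missing-data rates are assumed. The iAUC, GSH/GSSG and ATP/AMP analyses are not affected, nor is the after-exercise NAD+ model if it uses one change per period.

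**What to change.** In SAP 2.2.1 (before-exercise model) and 2.2.2 items 1 (point-by-point), 4 and 5:

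- Add a random intercept for period nested in subject, or state a within-period residual covariance.
- Specify Kenward-Roger or Satterthwaite degrees of freedom.
- In the ANCOVA models, name the period's own Day 1 value as the covariate.

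For the primary endpoint, choose one of two tests. Either add treatment-by-visit to the corrected model and test the Day 8 contrast, or analyse the Day 8 value alone with Day 1 as covariate. The second uses one record per subject-period and removes the problem; Days 3 and 5 then become supportive. For the OGTT, the planned iAUC comparison is already sound.

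The cost is one model term and a few words of SAP text, with no new data or visits. Confidence intervals will widen: in the three-visit ANCOVA simulations the true standard error was 1.1 to 1.5 times the model's for ICC 0 to 0.3.
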